Title: Regenerative Collagen Scaffold for Breast Volume Restoration in Breast-Conserving Surgery

NCT No: NCT07219316

Date: March 04, 2026

INTRODUCTION

Breast-conserving surgery (BCS) has become the standard surgical approach for early-stage breast cancer, offering oncologic outcomes equivalent to mastectomy while preserving the native breast mound. Despite its advantages, excision of tumor-bearing tissue frequently results in postoperative volume deficits, contour deformities, and asymmetry, which can significantly compromise cosmetic outcomes and patient quality of life. These deformities are particularly impactful in small- to moderate-volume breasts, where even modest tissue loss may produce visible distortion [1].

Traditional strategies for managing post-BCS volume loss include volume displacement techniques, regional or local flaps, autologous fat grafting, and, less commonly, implant-based approaches. While effective in selected cases, these methods are associated with important limitations. Flap-based reconstruction increases operative complexity and donor-site morbidity, fat grafting is limited by unpredictable resorption and the need for repeat procedures, and implants are generally unsuitable for partial defects and may interfere with radiotherapy and oncologic surveillance [2]. Consequently, there remains an unmet clinical need for minimally invasive, biologically compatible solutions capable of restoring volume while preserving breast architecture and oncologic safety.

The ideal volume restoration strategy following breast cancer resection in BCS would combine several key features: (1) immediate structural support to prevent cavity collapse, (2) biological integration promoting neovascularization and tissue regeneration, (3) minimal additional surgical morbidity, (4) compatibility with adjuvant radiotherapy, (5) preservation of imaging interpretability for cancer surveillance, and (6) predictable, durable cosmetic outcomes. Currently, no single technique fulfills all these criteria, highlighting a critical gap in oncoplastic breast surgery that regenerative biomaterials may address.

Regenerative medicine approaches have gained increasing attention as alternatives to traditional reconstruction. Among these, collagen-based scaffolds have emerged as promising tools due to their ability to provide immediate structural support while simultaneously promoting host tissue integration, neovascularization, and gradual remodeling. Type I collagen, the principal structural protein of the extracellular matrix, plays a central role in wound healing and tissue regeneration by supporting fibroblast migration, angiogenesis, and organized tissue deposition [3, 4].

An evolution in collagen biomaterials, un-crosslinked High-purity Type I collagen (HPTC) with added bioactivity through phosphorylation is characterized by reduced antigenicity, and predictable biodegradation and reliable tissue integration. Extensive clinical experience with HPTC-based constructs in complex wound environments has demonstrated their capacity to facilitate durable tissue regeneration across a range of indications. Early work describing novel collagen application techniques over meshed split-thickness skin grafts highlighted improved graft stability and wound coverage in challenging defects, establishing the biological versatility of collagen scaffolds in surgical reconstruction [1]. Subsequent clinical series demonstrated the successful use of collagen-based matrices as alternatives to flap coverage for exposed bone and tendon, further supporting their load-bearing and regenerative capabilities [2].

Randomized controlled trials conducted by our group and others have consistently shown superior or comparable outcomes with HPTC-based skin substitutes compared with dehydrated human amnion/chorion membrane (dHACM) in diabetic foot ulcers, venous leg ulcers, and pressure ulcers, with advantages in healing rate, tissue quality, and safety profile [3-7]. These findings have been reinforced by multicenter trials and systematic reviews demonstrating favorable histopathological remodeling, angiogenesis, and epithelialization with HPTC use in chronic wounds [8]. Beyond wound care, collagen-based biomaterials have also shown efficacy in complex surgical scenarios, including the management of infected prosthetic meshes, where collagen matrices facilitated tissue incorporation and infection resolution without foreign-body complications [9].

Collectively, this body of evidence underscores the biological consistency of HPTC scaffolds across diverse tissue environments, suggesting potential applicability beyond surface wounds to deeper soft-tissue defects. The breast excision cavity following BCS represents a uniquely suitable target for such regenerative scaffolds, as it requires immediate volume support, predictable integration, compatibility with adjuvant radiotherapy, and preservation of imaging interpretability for cancer surveillance [10,11].

Despite encouraging preclinical and early clinical data on collagen-based fillers for soft-tissue reconstruction, prospective human studies evaluating HPTC scaffolds specifically for breast volume restoration after BCS remain limited [12, 13]. Furthermore, standardized radiologic and volumetric outcome measures assessing scaffold integration and volume

maintenance in the breast are lacking. Addressing these gaps is essential to establish the clinical role of regenerative scaffolds within oncoplastic breast surgery.

The present prospective, multicenter clinical trial was therefore designed to evaluate the safety, efficacy, radiologic integration, volumetric stability, cosmetic outcomes, and patient-reported satisfaction associated with implantation of a high-purity Type I collagen scaffold for immediate volume restoration following breast-conserving surgery. By integrating objective imaging-based metrics with validated patient-reported outcomes, this study aims to provide comprehensive evidence supporting the use of HPTC scaffolds as a regenerative alternative to conventional volume-replacement techniques in breast cancer surgery.

MATERIALS AND METHODS

Study Design and Setting

This prospective, single-arm, multicenter clinical trial was conducted at two tertiary care academic institutions in Karnataka, India: JSS Medical College and Hospital, Mysuru. And Adichunchanagiri Institute of Medical Sciences (AIMS), B. G. Nagara. The study was designed to evaluate the safety, volumetric efficacy, radiologic integration, cosmetic outcomes, and patient-reported satisfaction following implantation of a High Purity Type I collagen (HPTC) scaffold for immediate volume restoration after breast cancer resection surgery. The trial was registered prospectively with ClinicalTrials.gov (ID: NCT07219316) and approved by the Institutional Ethics Committee (Approval No.: AIMS/IEC/240/2025).

The trial was conducted in accordance with the principles of the Declaration of Helsinki and Good Clinical Practice guidelines. Approval was obtained from the Institutional Ethics Committees of both participating centers prior to patient enrollment. Written informed consent was obtained from all participants. The methodological framework, outcome hierarchy, and statistical rigor were modeled on previously published multicenter HPTC trials to ensure internal validity and reproducibility.

Patient Selection and Eligibility Criteria

Women aged 18 to 70 years undergoing BCS for stage 0–II breast carcinoma or high-risk premalignant breast lesions were screened for eligibility. Patients were required to have a unifocal lesion suitable for wide local excision with an anticipated postoperative breast volume deficit of at least 20%, as estimated intraoperatively by the operating surgeon. Adequate skin envelope viability and the ability to undergo serial MRI examinations were mandatory.

Exclusion criteria included multicentric disease requiring mastectomy, prior radiotherapy to the ipsilateral breast, active local or systemic infection, known hypersensitivity to collagen-based products, autoimmune or connective tissue disorders, uncontrolled systemic illness, pregnancy or lactation, and inability to comply with postoperative follow-up or patient-reported outcome assessments.

Sample Size Determination

This study was designed as a prospective feasibility and early efficacy trial. Sample size was determined based on precision estimation for the primary composite endpoint rather than traditional hypothesis testing. Assuming a true success rate of 75% (based on oncoplastic literature), a sample of 40 patients provides an expected 95% confidence interval width of approximately 25%, which was deemed acceptable for preliminary efficacy assessment and effect size estimation to inform future definitive trials. The sample size also ensures adequate power (>80%) to detect a clinically meaningful difference of 15% in volume retention compared to the benchmark of 75%, assuming a standard deviation of 10% and $\alpha = 0.05$.

Surgical Technique and Intervention

All patients underwent standard oncologic breast-conserving surgery performed by experienced breast or plastic surgeons at the respective centers. Following tumor excision with confirmed hemostasis and margin adequacy, the excision cavity was carefully assessed for volume deficit and three-dimensional geometry.

A high purity Type I collagen scaffold was trimmed intraoperatively to conform precisely to the dimensions of the surgical cavity and implanted without tension. The scaffold was positioned in direct contact with surrounding viable breast tissue to facilitate cellular infiltration and neovascularization. No additional fixation beyond absorbable sutures was routinely required. Layered parenchymal and skin closure was performed using standard techniques. The use of surgical drains was left to the discretion of the operating surgeon based on oncologic considerations rather than scaffold placement.

Postoperative management, including antibiotics, wound care, chemotherapy, and radiotherapy, followed institutional breast cancer treatment protocols.

Outcome Measures

Primary Outcome: Breast Volume Restoration Success

The primary efficacy endpoint was breast volume restoration success at two months postoperatively, defined as a composite outcome incorporating both objective volumetric preservation and patient-perceived cosmetic satisfaction. Success required achievement of at least 80% objective breast volume retention relative to the immediate postoperative baseline, together with a patient satisfaction score of ≥ 7 on a 10-point Likert scale. This composite

endpoint was selected to ensure that structural volume preservation translated into clinically meaningful cosmetic benefit and patient acceptance.

Objective Breast Volume Retention

Objective breast volume retention was assessed using a dual-modality approach comprising three-dimensional surface photogrammetry and magnetic resonance imaging (MRI) volumetry. Baseline measurements were obtained within 48 hours postoperatively and repeated at 2, 4, and 8 weeks. Breast volumes were calculated for the operated breast and normalized against the immediate postoperative volume to derive percentage volume retention. MRI volumetry served as the reference standard, while 3D surface imaging provided adjunctive validation and assessment of symmetry.

Volume retention was expressed as a continuous variable and analyzed longitudinally to assess temporal stability and controlled scaffold resorption.

MRI Integration Score (MIS)

Radiologic integration of the HPTC scaffold was evaluated using a predefined MRI Integration Score (MIS), a composite semi-quantitative scoring system developed to assess biological scaffold performance. MRI examinations were performed immediately postoperatively and at 4 and 8 weeks using standardized T1-weighted, T2-weighted, and dynamic contrast-enhanced sequences.

The MIS evaluated four domains: scaffold–host tissue integration, neovascularization based on enhancement patterns, scaffold resorption and volume replacement, and tissue quality within the scaffold region. Each domain was scored from 0 to 3, yielding a total score ranging from 0 to 12, with higher scores indicating superior integration and regenerative remodeling.

Cosmetic Outcome: BREAST-Q

Cosmetic outcomes were assessed using the BREAST-Q questionnaire [14], a validated patient-reported outcome measure specific to breast surgery. The “Satisfaction with Breasts” domain was prespecified as the primary cosmetic endpoint. Questionnaires were administered preoperatively and at 4 and 8 weeks postoperatively. Raw scores were converted to standardized scores ranging from 0 to 100 according to BREAST-Q scoring manuals, with higher scores indicating greater satisfaction [14].

Improvement over baseline and attainment of an absolute score ≥ 70 at final follow-up were considered clinically meaningful cosmetic outcomes.

Safety and Complications

Safety assessment included prospective recording of all adverse events and postoperative complications, including seroma, surgical site infection, hematoma, wound dehiscence, scaffold migration or exposure, and delays in adjuvant oncologic therapy. Device-related serious adverse events were specifically monitored. All events were managed according to institutional protocols and documented throughout the follow-up period.

Data Collection and Follow-up

Baseline demographic data, tumor characteristics, operative details, and immediate postoperative imaging were recorded at enrollment. Follow-up assessments were conducted at 2, 4, and 8 weeks postoperatively, during which volumetric measurements, MRI evaluation, BREAST-Q questionnaires [14], and complication surveillance were completed. Data were recorded in standardized case record forms at both centers to ensure uniformity.

Statistical Analysis Plan

Statistical analysis was performed using IBM SPSS Statistics (version 28.0). Continuous variables were summarized as mean \pm standard deviation, while categorical variables were expressed as frequencies and percentages. Longitudinal changes in breast volume retention, MRI Integration Score, and BREAST-Q scores were analyzed using repeated-measures analysis of variance. One-sample t-tests were used to compare observed volume retention against predefined clinical benchmarks. Correlations between objective volumetric outcomes and patient-reported satisfaction were assessed using Pearson correlation coefficients. A two-sided p value of less than 0.05 was considered statistically significant.

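### The repeated-measures ANOVA p value cannot establish either stable volume or controlled resorption, and the plan sets no margin or limit for either conclusion

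*Combined protocol and SAP*

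**What the plan says.** The closing paragraph of the Introduction lists volumetric stability among the trial's aims: the trial is to "evaluate the safety, efficacy, radiologic integration, volumetric stability, cosmetic outcomes" and patient-reported satisfaction.

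Under Objective Breast Volume Retention, each volume of the operated breast is "normalized against the immediate postoperative volume to derive percentage volume retention", so every patient's baseline value is 100%. On timing: "Baseline measurements were obtained within 48 hours postoperatively and repeated at 2, 4, and 8 weeks". On purpose, retention is treated as continuous and "analyzed longitudinally to assess temporal stability and controlled scaffold resorption".

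The Statistical Analysis Plan gives one longitudinal method: "Longitudinal changes in breast volume retention, MRI Integration Score, and BREAST-Q scores were analyzed using repeated-measures analysis of variance". Its decision threshold is general: "A two-sided p value of less than 0.05 was considered statistically significant".

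Neither section says how small a change counts as stable, how much loss is still controlled, or which ANOVA result would be unfavourable.

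The same variable is also used elsewhere. The primary composite needs retention of 80% or more at two months. The Statistical Analysis Plan adds one-sample t-tests of retention against benchmarks, and Sample Size Determination names a benchmark of 75%. One domain of the MRI Integration Score (MIS), scored 0 to 3, covers scaffold resorption and volume replacement.

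**The concern.** A repeated-measures ANOVA tests whether mean retention is equal across visits. Two conclusions are to be drawn from it, and it is built for neither.

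- **Stability** is a claim that change is small. Failing to reject equal means does not show this, because the test may simply lack power for the loss that occurred.
- **Controlled resorption** is a claim that loss stayed within a limit. Rejecting equal means shows only that some change occurred. Its size is not judged against anything.

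At stake is a stated objective. As written, a report could describe volume as stable after a non-significant test although a real loss had occurred, or describe a significant fall as controlled without having said beforehand what uncontrolled would look like.

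**Working it through.** **Inputs from the documents.** n = 40, and SD of retention 10 points (Sample Size Determination); visits at weeks 2, 4 and 8 (Objective Breast Volume Retention); two-sided alpha 0.05 (Statistical Analysis Plan).

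**Assumptions.** The SD of 10 applies at each visit. Within-patient correlation ρ is equal between all visits and is 0.3, 0.5 or 0.7; the documents give none. Loss is linear in weeks, and no data are missing. Baseline is left out of the ANOVA because it is 100% for everyone; the plan does not say whether it is included.

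**1. The plan's own power figure.** For a 15-point difference from 75%, the noncentrality is (15/10) × √40 = 9.49, and power exceeds 0.999. The stated figure of more than 80% holds, but it concerns the level against a benchmark. The plan gives no figure for change between visits.

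**2. What a non-significant ANOVA shows.** For a loss of L points from week 2 to week 8, the visit means are 0, −L/3 and −L, with average −4L/9. The sum of squares about that average is L² × (16 + 1 + 25)/81 = 0.5185 L². The noncentrality is

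λ = n × 0.5185 L² / [SD² × (1 − ρ)],

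referred to F with 2 and 78 degrees of freedom (critical value 3.11). For L = 5 and ρ = 0.5, λ = 40 × 12.96 / 50 = 10.37, and the miss rate is 19%.

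| True loss, weeks 2 to 8 | Missed, ρ = 0.3 | Missed, ρ = 0.5 | Missed, ρ = 0.7 |
|---|---|---|---|
| 3 points | 72% | 62% | 42% |
| 4 points | 53% | 39% | 16% |
| 5 points | 34% | 19% | 4% |
| 8 points | 2% | 0.3% | <0.1% |

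The problem therefore concerns small and moderate losses. Losses of 8 points or more are almost never missed.

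**3. What a significant ANOVA shows.** Take a linear path starting at 98% at week 2. A fall to 90% by week 8 gives p<0.05 with probability 0.98 to 1.00. A fall to 80%, 65% or 50% gives it with probability about 1.00. The p value does not separate these courses. Conversely, retention flat at 60% from week 2 to week 8 gives p<0.05 only 5% of the time.

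**4. Sensitivity to including baseline.** Extend the 5-point path back to baseline at the same weekly rate (a further 5/3 = 1.7 points) and add baseline as a fourth level. The miss rate at ρ = 0.5 then falls from about 19% to about 4%, and the plateau at 60% would be detected. Step 3's first problem remains: a significant result still has no size attached to it.

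**5. What an interval would give.** For a paired change between two visits, the SD is 10 × √[2(1 − ρ)] = 11.8, 10.0 or 7.7. The 95% half-width is 2.023 × SD/√40 = 3.8, 3.2 or 2.5 points. With an illustrative margin of −5 and no true change, the noncentrality is 5 ÷ (SD/√40) = 2.67, 3.16 or 4.08. The lower limit then clears the margin about 74%, 87% or 98% of the time.

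**The case against.** The strongest reply is that retention does face criteria that can fail. With a week-8 mean of 65% and SD 10, only about 7% of patients would reach 80%, and the t-test against 75% would be significant in the unfavourable direction with power above 0.999. Because retention is normalised to each patient's own baseline, a week-8 benchmark test is also, in effect, a test of total change since surgery. Continuous variables are reported as mean and SD, so the size of a fall would be visible.

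All of that stands. A reader might infer that no result can count against the scaffold; the documents do not support that. But these criteria do not fill the gap. They set a floor for the level and say nothing about change between visits. The floor is also far from stability: a mean loss of 20 points by week 8 (retention 80%, SD 10) would be significantly better than the 75% benchmark with power 0.87.

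A reader might also infer that the plan commits to calling a null result stability and a significant fall controlled resorption. It contains no such rule. The defect is that no rule is given. A significant rise would fit neither label.

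Nor are the two aims necessarily contradictory. Retention measures the whole breast, and a scaffold that resorbs while host tissue replaces it could leave breast volume unchanged. That is a reason not to read scaffold resorption from whole-breast volume.

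Finally, this is a secondary analysis in a feasibility trial sized for its primary composite. That limits the weight of the point but does not remove it, because stability is a named objective.

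**Conclusion.** The concern holds for the longitudinal analysis, and the plan should be changed. The ANOVA p value cannot establish stability, because a true 5-point loss is missed about 34%, 19% or 4% of the time at correlations of 0.3, 0.5 or 0.7. It cannot establish controlled resorption, because modest and severe losses give the same result.

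The miss rates rest on the plan's SD applying at every visit, equal correlations, a linear course, complete data and baseline being left out. They would be lower with higher correlation or with baseline included, and higher with dropout. The logical point rests on none of these assumptions.

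The primary endpoint is not affected. The benchmark tests and the 80% threshold remain able to show poor retention.

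**What to change.** In Objective Breast Volume Retention and the Statistical Analysis Plan, base the stability conclusion on estimates with 95% confidence intervals instead of the ANOVA p value:

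1. Report mean change from the immediate postoperative baseline to week 8 (mean week-8 retention minus 100), so that early loss followed by a plateau is visible.
2. Report mean within-patient change between named follow-up visits with MRI volumes, for example week 4 to week 8. First reconcile the visit lists: the volume section has measurements at 2, 4 and 8 weeks, whereas the MIS section schedules postoperative follow-up MRI at 4 and 8 weeks only.
3. Claim stability only if the lower 95% limit lies above a margin that the sponsor justifies and fixes before analysis. Name the interval to which the claim applies, and print the change from baseline beside it. Otherwise give the size of the change with its interval and make no stability claim.
4. If the margin is met but the interval also excludes zero on the side of loss, report a loss smaller than the margin. This can happen: at correlation 0.8 the half-width is 2.0 points, so an observed change of −2.5 gives −4.5 to −0.5, which clears a −5 margin and excludes zero.
5. Do not conclude controlled scaffold resorption from whole-breast retention alone. The MIS resorption domain addresses resorption separately.

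The cost is a few sentences, with no added patients or measurements. The price is that a margin must be defended and the claim can fail, even for a scaffold with no true loss, at the rates shown in step 5 of the working. The −5 used there is only an illustration; the documents supply no margin.

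### Repeated-measures ANOVA loses any patient with a missed visit, and the plan gives neither a missing-data rule nor the time levels, although baseline retention is 100% by definition

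*Combined protocol and SAP*

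**What the plan says.** The Statistical Analysis Plan section gives one method for three outcomes: "Longitudinal changes in breast volume retention, MRI Integration Score, and BREAST-Q scores were analyzed using repeated-measures analysis of variance". The software is SPSS 28. The procedure within it, the levels of the time factor, any sphericity correction, the analysis set and the handling of missed visits are not stated. The significance rule is general: "A two-sided p value of less than 0.05 was considered statistically significant".

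The three outcomes have different schedules and different kinds of baseline:

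- **Volume retention** (Objective Breast Volume Retention): measured within 48 hours of surgery and at weeks 2, 4 and 8. Volumes are "normalized against the immediate postoperative volume to derive percentage volume retention". The section gives the aim of the longitudinal analysis as judging whether volume holds steady over time and whether the scaffold resorbs in a controlled way.
- **MIS** (MRI Integration Score): "MRI examinations were performed immediately postoperatively and at 4 and 8 weeks". Four domains are scored 0 to 3, for a total of 0 to 12. No expected baseline value is given.
- **BREAST-Q** (Cosmetic Outcome): before surgery and at weeks 4 and 8. Its baseline is a measured score that varies between patients.

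**The concern.** Two features of the method deserve attention.

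The first is completeness. A patient who misses one visit contributes nothing to a classical repeated-measures ANOVA, including the visits that were attended. With 40 patients this wastes data. If patients who miss visits also tend to have lower retention, the curve from the remaining patients is too favourable.

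The second is the meaning of the time effect for retention. Dividing each volume by the patient's own baseline makes the baseline value 100% with zero variance. If this constant enters as a time level, an early drop followed by complete stability gives a significant time effect, just as continuing loss would. The p-value then cannot separate the two patterns that the analysis is meant to tell apart.

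A related, weaker issue touches MIS. A scaffold scored straight after implantation has had little time to integrate or vascularise, so a rise from that scan is likely whatever the device's merit.

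**Working it through.** **The plan's own figure.** Sample Size Determination says: "The sample size also ensures adequate power (>80%) to detect a clinically meaningful difference of 15% in volume retention", against a benchmark of 75% with SD 10%. With n = 40 the standard error is 10/√40 = 1.58, and power ≈ Φ(15/1.58 − 1.96) = Φ(7.53) > 0.9999. The figure is met with room to spare. It concerns a one-sample mean, not the ANOVA. The SD of 10 and n = 40 are reused below.

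**1. Patients lost to incomplete rows.** Inputs: n = 40 (Sample Size Determination); k = 3 follow-up visits for volume and k = 2 for MIS and BREAST-Q (outcome sections); m = missed-visit rate, assumed. Under independence the complete cases number 40 × (1 − m)^k.

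| m (assumed) | k = 3 | k = 2 |
|---|---|---|
| 2% | 37.6 | 38.4 |
| 5% | 34.3 | 36.1 |
| 10% | 29.2 | 32.4 |
| 20% | 20.5 | 25.6 |

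If the same patients missed every visit, the loss would be smaller: 40 × 0.95 = 38 or 40 × 0.90 = 36 would remain.

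At m = 10% and k = 3, the observed follow-up values number 40 × 3 × 0.9 = 108. Complete cases keep 29.16 × 3 ≈ 87.5, so 20.5/108 = 19% of the collected values are discarded. For a week-8 mean with SD 10, the 95% CI half-width t × 10/√n is 3.8 points with 29 patients and 3.4 with the 36 expected to have a week-8 value.

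Bias was examined in an assumed dropout model: 10% to 20% missing at week 8, the odds of missing doubling per SD lower week-4 retention, and correlation 0.5 to 0.9. Complete cases overstated week-8 retention by 0.3 to 1.2 points. An estimate using the week-4 data of all patients was within 0.01 of the truth.

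**2. Baseline as a time level.** Take true means of 100, 90, 90, 90, which is perfect stability after surgery.

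- Grand mean: (100 + 90 + 90 + 90)/4 = 92.5.
- Time sum of squares: 40 × (7.5² + 3 × 2.5²) = 40 × 75 = 3000; mean square 3000/3 = 1000.
- Expected error mean square, with baseline variance 0, follow-up variance 100 and between-visit correlation ρ: [300 − (300 + 600ρ)/4]/3 = 75 − 50ρ. This is 60 at ρ = 0.3, 50 at 0.5 and 30 at 0.9.
- Ratio: 1000/60 = 16.7, 1000/50 = 20 and 1000/30 = 33, against a 5% critical value of 2.68 on 3 and 117 degrees of freedom.

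Simulation (20,000 runs, n = 40, SD 10, ρ from 0.3 to 0.9) agrees:

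| True retention | Baseline as a level | Weeks 2, 4, 8 only |
|---|---|---|
| Flat at 90% | 100% reject | 4.9% to 5.1% reject |
| Flat at 95% | 88% to 91% reject | not run; a common shift does not alter this test |

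**3. Sphericity.** With true retention at 100% throughout and baseline as a level, uncorrected type I error was 4.9% to 5.7% for ρ of 0.3 to 0.7, about 6.5% at 0.8 and 8.1% at 0.9. With the Greenhouse-Geisser correction it was 4.5% to 5.0%.

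**4. A schedule point that affects k.** Volumetry is set at weeks 2, 4 and 8 with MRI as the reference standard. The MIS section schedules MRI at weeks 4 and 8 only, while Data Collection and Follow-up implies MRI at all three visits. If there is no week-2 MRI, the MRI volume outcome has two follow-up visits, and an ANOVA that included week 2 would have no complete rows. These passages need to be reconciled.

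**The case against.** The strongest reply is that the plan does not say baseline is a time level. An ANOVA on weeks 2, 4 and 8 fits the text equally well, and the second problem then disappears. That stands: the result in step 2 is conditional. What remains is that the plan leaves open a choice on which the meaning of the test depends.

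The missed-visit rates are assumed. Follow-up lasts only eight weeks, the eligibility criteria exclude patients unable to comply with it, and clustered misses cost fewer patients than independent ones. The counts are therefore illustrations over a range, not forecasts, and the bias in the assumed model is small.

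Three stronger readings are tempting, and the documents do not support them:

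- **The baseline MIS is fixed or must be near its floor.** It is a scored variable. No baseline value or scoring anchors are given, and how domains such as tissue quality would score on day 0 is unknown. A low value is a plausible inference only.
- **The zero-variance baseline makes the F-test seriously invalid.** The inflation is slight at most of the correlations examined, and the standard correction largely removes it.
- **The constant-baseline problem reaches all three outcomes.** BREAST-Q has a measured preoperative score, so only the loss of incomplete rows applies to it.

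**Conclusion.** The point holds in two parts. Without condition: the named method discards patients with any missed visit, and nothing in the documents offsets this. The size depends on an unknown rate. At 5% to 10% independent misses, 34 to 29 of 40 patients remain for volume (if week 2 is measured) and 36 to 32 for MIS and BREAST-Q.

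Conditional on baseline being a time level: the retention test cannot show whether volume is stable, because a flat 90% is rejected essentially always. This rests on n = 40, SD 10 and equal variances and correlations across follow-up visits. The margin is too wide for the choice of correlation to matter.

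A reader might infer that the main efficacy result is compromised. It is not: the primary composite at two months is not assigned to this ANOVA, and benchmark comparisons of retention use one-sample t-tests. The change should be made because it is cheap and improves three supporting analyses.

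**What to change.** Replace the ANOVA with a mixed model for repeated measures, available in the same software:

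- **Volume retention:** percentage retention as the plan defines it, post-baseline visits only, visit as fixed effect, unstructured covariance, all patients with at least one post-baseline value. Report week-8 mean retention with 95% CI and the between-visit change. Keep the percentage scale: a log-ratio outcome would turn the arithmetic mean into a geometric one and no longer match the benchmark comparison.
- **BREAST-Q:** the same model for change from the preoperative score, with that score as covariate.
- **MIS:** make the week-8 score with 95% CI and the week 4-to-8 change the main results. A rise from the immediate postoperative scan may be described but is weak evidence of performance.
- **Missing data:** state that the model assumes missingness depends only on observed data, and report the number of patients observed at each visit.

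If ANOVA is kept, list the time levels for each outcome, leave the 100% baseline out for retention, name a sphericity correction and add a missing-data rule.

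The cost is revised SAP wording and slightly more programming.
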